## Methods and Procedures Applied to Human Subjects

**Entered:** 01/03/18 **By:** [name] **Internal:** No

In addition to listing each university's resources to provide participants after each data collection period, please include some national resources as well (hotlines, websites, etc.).

**Entered:** 01/03/18 **By:** [REDACTED] **Internal:** No

I have added a sentence : "In addition to the university resources, national resources such as hotlines and websites will also be included that focus on stress and anxiety."

After initial correspondence and site approval/IRB approval obtained then the researcher will arrange a time to introduce the study. The researcher will offer to come to each school to introduce the study or offer a Zoom or pre-recorded video to introduce the study to the pre-licensure baccalaureate nursing students. The researcher will provide the link to the nursing students or the nursing department designee may send the initial email invitation to the nursing students. The researcher will not be able to identify who received the initial email invitation to participate in the study. Student recruitment will start at the beginning of the Spring semester of 2018. The two group experimental design will collect data over the course of the spring academic semester. There will be three separate points of data collection. This is explained below.

Senior-level pre-licensure baccalaureate nursing students will access Qualtrics® via a link provided by the email invitation or offered by the researcher in person, Zoom, or on a pre-corded video. Implied consent will be established if a nursing student selects "yes" on the consent page in Qualtrics®. Contact information for the researcher and dissertation chair will be made available on the informed consent on Qualtrics®. After reviewing the consent and indicating intent to participate, potential study participants will then proceed directly survey tools. There are three data collection time periods within the study (1st two weeks of the semester, after the 5th text message, and within the last month of the semester). The two main tools used in the study have been found to be valid and reliable: The State-Trait Anxiety Inventory and the Health-Promoting Lifestyle Profile-II. I have attached the demographic questionnaire, HPLP-II, and the open-ended questions. Here is a breakdown of the tools used during each of the three data collection time periods:

The first two weeks of the semester:

- Demographic questionnaire (12 questions)

*Describe exactly will happen with the subjects from the time of their first contact until the time of their last contact. What will participants actually do while participating in the project?*

- State-Trait Anxiety Inventory State subscale (20 questions)
- State-Trait Anxiety Inventory Trait subscale (20 questions)
- Two subscales of the Health-Promoting Lifestyle Profile-II: stress management and interpersonal relations (17 questions)
- Total of 69 questions

After the 5th text message was distributed:

- State-Trait Anxiety Inventory State subscale (20 questions)
- Two subscales of the Health-Promoting Lifestyle Profile-II: stress management and interpersonal relations (17 questions)
- Total of 37 questions

Within the last month of the semester:

- State-Trait Anxiety Inventory State subscale (20 questions)
- Two subscales of the Health-Promoting Lifestyle Profile-II: stress management and interpersonal relations (17 questions)
- Open-ended questions on self-care (6 questions)
- Total of 43 questions

On each survey, nursing students will be asked to enter their email address. On the first demographic questionnaire, students will provide their ten-digit cell phone number for potential distribution of the text messages. Senior-level pre-licensure baccalaureate nursing students will be told to consistently use the same email address throughout the study. The email address provided by the senior-level pre-licensure baccalaureate nursing students will be used to distribute these tools and to link the responses. The ARL will initiate a link provided for the remaining two data collection times. Implied consent will continue to be established each time the nursing student selects "yes" on the consent page in Qualtrics®. Contact information for the researcher and dissertation chair will be made available on the informed consent on Qualtrics®. At the conclusion of each survey, a list of resources at their school will be provided to help them with stress and anxiety. This list will be obtained through a through look at each college or university's website. In addition to the university resources, national resources such as hotlines and websites will also be included that focus on stress and anxiety.

Nursing students will be reminded that their participation is voluntary throughout the study and they have the right to withdraw from the study at any time. The nursing department designee will send a reminder email within 72 hours of the initial study invitation. For the second and third data collection times, senior-

level pre-licensure baccalaureate nursing students will have 72 hours to complete the tools. After the 72 hours, an email reminder will be sent to the study participants to complete the tools within the next 72 hours for the second and third distribution. Since the email addresses will not be known for the first data collection time, an email reminder can not be sent. Study participants will have one week to complete the instruments from the initial email distribution. Qualtrics® is a password protected online survey program. The researcher will create the surveys, reminders, and text messages in Qualtrics® and will hand over the distribution to the ARL. The ARL will distribute and have access to the data and email addresses and will link the responses during the study period. During this time, the researcher will not have access to the data and will receive a de-identified file with the study data merged from the ARL. Throughout the study, the identifiable information will remain anonymous to the researcher. Additionally, the phone numbers and email addresses will also remain anonymous to the researcher.

The randomization of schools will be established prior to the first data collection. Each school will be considered a unit and will be randomized to either the intervention or control group. After the initial data collection, pre-licensure baccalaureate nursing students randomized to the intervention will receive text messages distributed from Qualtrics® throughout the semester.

The researcher anticipates 10 text messages will be sent to the senior-level pre-licensure baccalaureate nursing students. Nursing students will not receive any in-person or online form of education. The text messages will be no longer than 160 characters and will be created from the ANA's book *Self-Care and YOU: Caring for the Caregiver* (Richards, Sheen, & Mazzer, 2014). The messages were reviewed by a content expert. The text message will be sent from Qualtrics® by using a carrier text message. The email messages and distribution times will already be loaded into Qualtrics® prior to the ARL taking over the distribution.

Every nursing student in the intervention group will receive the same text message to ensure consistency. Each text message will also come with a link that will provide additional resources for the student at their institution. This will be the same information that is provided for the student at the conclusion of each survey. The nursing students will click on the link that is described by saying "The link will provide you will a list

of resources available on your campus". Pre-licensure baccalaureate nursing students who receive the text messages will have the option to unsubscribe from the text message by clicking on a link within the message. The verbiage states "Click here to unsubscribe". At the conclusion of the study, senior-level pre-licensure baccalaureate nursing students who were in the control group will have the option to receive a Microsoft® Word document containing the text messages to their email address.

Baccalaureate nursing students will have the option to be entered into a random drawing for a gift card at the conclusion of each survey. At the bottom of the page, they will click "Yes" that they want to be entered into the drawing. They will be directed to a separate survey to enter in their email address. The gift card survey and the study survey are two separate surveys and will not be linked. This will remain anonymous to the researcher. The ARL will assist in the distribution of the Amazon giftcards.

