## Method of Subject Selection

The setting for this study will be up to six public or private universities located in the Mid-Atlantic region. All potential schools of nursing have a traditional four-year baccalaureate degree in nursing program. The potential schools were identified through a review of the NCLEX-RN Performance of First Time Candidates Educated in Pennsylvania who Completed NCLEX in the U.S. published by the National Council of State Boards of Nursing. Nursing programs who had at least 50 graduates who were eligible to take the NCLEX in 2017 will be recruited. In Pennsylvania, 24 schools of nursing are eligible to be recruited based on these requirements. From the 24 schools of nursing in Pennsylvania, eight nursing schools were excluded because they have a PhD program. Pennsylvania State University has multiple campuses that offer traditional BSN programs. Two of the campuses will be excluded because they offer PhD programs (University Park & Hershey). However, this leaves five satellite campuses that may be recruited from. If none of these 16 schools of nursing are agreeable to participate, the researcher will look to other traditional baccalaureate nursing schools in the Mid-Atlantic region.

An email will be sent to the nursing chairs or faculty contact at each of the 16 eligible schools of nursing in Pennsylvania. The email will describe the research study purpose, timeline, and ask if the nursing chair or faculty contact would be interested in being a study site. If the nursing chair or faculty contact is agreeable, an in-person or telephone meeting will be offered to discuss the project. The first six schools of nursing who are agreeable to participate will be used for the study. Site approval or site IRB approval will be completed at each institution.

The researcher will go to each school in-person, provide a Zoom session, or offer to pre-record a video to introduce the study and provide the initial link to the pre-licensure senior-level baccalaureate nursing students. If the school would rather have the nursing secretary or site designee at the school distribute an initial email, the researcher will provide a pre-recorded video to explain the study. Student recruitment will start at the beginning of the Spring semester of 2018.

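### Schools are allocated before any student consents, and nothing keeps the arm from the people who recruit, so selective enrolment is possible and cheap to prevent

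*Protocol*

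**What the plan says.** On allocation, Methods and Procedures Applied to Human Subjects states "Each school will be considered a unit and will be randomized to either the intervention or control group", and on timing "The randomization of schools will be established prior to the first data collection". Schools enter by order of agreement: "The first six schools of nursing who are agreeable to participate will be used for the study" (Method of Subject Selection).

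On recruitment, "Student recruitment will start at the beginning of the Spring semester of 2018". The approach to students is described as "The researcher will go to each school in-person, provide a Zoom session, or offer to pre-record a video to introduce the study". Alternatively, a department designee may send the invitation, and the designee also sends a reminder within 72 hours. On consent, "After reviewing the consent and indicating intent to participate, potential study participants will then proceed directly survey tools". The three measurement points are "1st two weeks of the semester, after the 5th text message, and within the last month of the semester".

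On the intervention, "After the initial data collection, pre-licensure baccalaureate nursing students randomized to the intervention will receive text messages".

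The safeguards described concern identities, data and distribution. The ARL distributes surveys and messages, links responses and de-identifies the file. The Privacy/Confidentiality section bars the researcher from data and distributions until the study closes. Who draws the school allocation, who holds it, and from whom it is kept are not stated.

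**The concern.** When whole schools are randomised and students volunteer afterwards, randomisation protects the comparison only if joining does not depend on the arm. A recruiter who knows that a school will receive messages may present the study, or follow up the invitation, differently from one who knows that it will not. The arms may then contain different kinds of volunteers before any message is sent.

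Two features make this matter here. There are at most six schools, so one or two schools with unusual recruitment can move an arm mean. The outcomes are self-reported state anxiety and health-promoting behaviours, which plausibly relate to why a student joins. Adjusting for the baseline score removes only the part of the imbalance that the score captures, not unmeasured reasons for joining.

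**Working it through.** The point rests on the order of procedures, so the main check sets the statements side by side.

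**Order of events**

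1. Schools agree to take part; up to six are used (Method of Subject Selection).
2. Schools are randomised before the first data collection (Methods and Procedures Applied to Human Subjects).
3. The researcher or designee introduces the study and invites students at the start of the semester. Whether the introduction precedes or follows step 2 is not stated.
4. Students consent and go straight into the baseline survey, within the first two weeks of the semester.
5. Messages begin after baseline.

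Step 4 is the first data collection, so step 2 precedes every student's consent, wherever the introduction falls.

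**Who could know the arm at step 4**

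| Person | Role while students decide | What the protocol restricts |
|---|---|---|
| Researcher | Introduces the study; builds messages and loads sending times before handover to the ARL | Data and distributions, not the allocation |
| School designee | May send the invitation; sends the reminder | Nothing stated |
| Student | Decides and answers baseline | Nothing stated, but the wording suggests the arm is not yet known |

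**Is the early draw needed?** No. Messages start after step 4, and the ARL already controls distribution.

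**Room for selective joining.** The protocol gives no figure on this point. Inputs: at least 50 graduates per school in 2017, 86 students needed and 100 sought. Assume that the 2018 senior class is about the size of that minimum.

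- Six schools: 6 × 50 = 300 seniors; 86/300 = 29%, 100/300 = 33%.
- Four schools (assumed, since six is a maximum): 4 × 50 = 200; 86/200 = 43%, 100/200 = 50%.
- Larger classes would lower these shares.

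Partial uptake leaves room for selection; it does not show that uptake differs by arm.

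**Illustration of the stakes.** The shift b between arms caused by selective joining is an assumption with no source in the documents. Take the planned 72 students as 36 per arm, a two-sided 5% test, no clustering and no baseline adjustment.

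- Standard error in SD units: √(2/36) = 0.236.
- False-positive rate: 1 − Φ(1.96 − b/0.236) + Φ(−1.96 − b/0.236).

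| Assumed b | b/0.236 | False-positive rate |
|---|---|---|
| 0.1 SD | 0.42 | 7% |
| 0.2 SD | 0.85 | 14% |
| 0.3 SD | 1.27 | 25% |

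Relative to the planned effect of .30, whose metric is not stated:

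- If it is Cohen's f, the difference is 2 × 0.30 = 0.60 SD, and a shift of 0.1 to 0.2 SD is 17% to 33% of it.
- If it is a standardised mean difference of 0.30 SD, the same shift is 33% to 67%.

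**The case against.** The strongest reply is that the protocol nowhere says anyone is told the arm. Drawing early is harmless if the result is concealed. The Privacy/Confidentiality section also keeps the researcher from the distributions, which differ by arm. This stands in part: knowledge of the arm is possible, not shown. But the restriction does not cover the allocation itself. The researcher prepares the messages before handover, and the designee is under no restriction.

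A reader might infer that students answer the baseline anxiety items knowing their arm. The documents do not support that. All students give a phone number for possible messages, and the Information Withheld section says controls will recognise their group when no messages arrive. Both suggest the arm becomes known after baseline. Biased baseline answers would need a leak that no section describes. The consent pages are not in the copy reviewed, so what they say about assignment cannot be judged.

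A reader might also take the varying mode of introduction (visit, Zoom or video) as evidence of selection. The protocol links the mode to what the school prefers, not to its arm. It adds variation between schools and proves no more.

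Finally, a single draw after every school's baseline has closed may be awkward, because the baseline window follows each school's semester and start dates may differ. That is a fair limit on the remedy, and the fix allows for it.

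**Conclusion.** The point holds as one of unstated concealment combined with early allocation. The stated order puts every enrolment after the school's arm is fixed, and nothing visible keeps the arm from those who recruit. Selective enrolment is therefore possible, up to six schools will not average it out, and analysis cannot fully undo it. The documents do not show that it would occur. Its size cannot be derived from them, and the 7% to 25% range depends entirely on the assumed shifts and the simplifications given with them. Bias in the baseline answers is a lesser, conditional risk.

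This concerns trial conduct, not analysis detail that could be left to a later plan. It has to be settled before students are invited.

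**What to change.** In Methods and Procedures Applied to Human Subjects, replace the sentence on the timing of randomisation with:

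> The ARL will randomise the participating schools, as evenly as their number allows, after the baseline survey has closed. Where semester dates differ, the ARL will hold the allocation and release each school's arm only after that school's baseline has closed. The researcher, school staff and students will not know the allocation before then.

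Add that the message set-up is prepared identically for all schools before handover to the ARL, so that preparing it cannot reveal the arm. The Information Withheld section should mention the temporary concealment, so that the two sections agree.

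The sample size does not change. The cost is a few sentences and one more task for the ARL, which already runs distribution. The first message may start slightly later at some schools. If all schools waited for the last baseline to close, the delay would depend on how far semester dates differ, which the protocol does not give; release school by school limits it.

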## Risks/Benefits

### Potential Risks

There are no direct risk for participation in the study.

*Describe the level of risk of the study to the participants, investigators, and any other group that might be impacted. You should compare the level of risk in your study and the federal definition of "minimal risk". "Minimal risk" is defined in 45 CFR46.1029(i) as "the probability and magnitude of harm or discomfort anticipated in the research are not greater in and of themselves than those ordinarily encountered in daily life or during the performance of routine physical or psychological examinations or tests." Visit the IRB website for more detail on this topic.*

### Protection Against Risks

They have the right to withdraw from the study at any time. If they withdraw from the study, all of the data will be destroyed and not used. All of the data will be distributed by the Applied Research Lab and will remain anonymous to the researcher.

*Discuss in detail how the investigators will provide safeguards against the identified risks.*

### Potential Benefits

There may be no direct benefits from participation in the study. However, the knowledge received may be valuable for nurse educators to help senior-level pre-licensure baccalaureate nursing students as they transition into the workforce. In addition, the study participants may become more aware of health promoting behaviors and this could improve their overall well-being.

*Discuss any potential benefits to the human subjects in the research.*

### Compensation for Participation

Study participants are eligible to be entered to win a Amazon gift card at the conclusion of each data collection time period. At the conclusion of survey, participants will be redirected to another survey to enter in their email address to be randomly entered into the giftcard drawing for Amazon. The gift cards will increase in value during each of the three data collection time points. There will be up to six giftcards distributed at each data collection time point. One gift card will be randomly selected from the participants at each study site. The first set of giftcards will be \$10.00, the second set will be \$20.00 each, and the third set of giftcards will be \$50.00 for a potential total of \$480.00 dollars worth of Amazon giftcards. Nursing students do have the option to not be entered into the drawing by selecting "no". The Applied Research Lab at IUP will randomize the winners and send the giftcard to study participants since the researcher will not have access to the participating students email addresses.

*Discuss any and all forms of compensation for participation. This includes payment, extra credit, chances at winning a gift card, etc. Discuss also how the research subject will receive this compensation.*

### Alternatives Participation

Nursing students are not required at their school of nursing to participate and will have access to the Microsoft Word document with the text messages at the conclusion of the study.

### Information Withheld

No information will be withheld. They will know if they are in the control group if they do not receive text messages during the research study.

*If information will be intentionally withheld from research subjects, discuss this here along with the rationale for doing so.*

### Debriefing

There will be no debriefing included in this study. However, the control group will receive a Microsoft Word document at the conclusion of the study with the ten text messages included.

*If any debriefing will be provided to the research subjects, please discuss it here.*

## Privacy/Confidentiality

Prospective senior-level pre-licensure baccalaureate nursing students will have the opportunity to withdraw from the research study at any time by contacting the ARL at Indiana University of Pennsylvania. Every time the senior-level pre-licensure nursing student receives the email invitation to complete the study tools, the study participant will be able to review the informed consent and decide if he or she would or would not like to participate. There is no anticipated risk for participation in this study. However, every student will receive a link to the list of local and institutional resources to assist if any psychological distress would occur. This list will also be provided to each nursing department chair. To minimize coercion, the researcher will not have access to any of the data or distributions until the study has closed. The informed consent that the students will access on Qualtrics® will address the benefits, risks, right to withdraw, and researcher contact information. Nursing students will be made aware that their participation in this study will have no impact on their grade nor will the faculty members know their acceptance or refusal to participate in the research study. Nursing students will not be awarded any extra credit and will not be asked any information about their health status or current mental health diagnosis, medications, or treatment during the study. Senior-level pre-licensure baccalaureate nursing students will have the option to enter to win a gift card during each of the three data collection periods. The students will be directed to a separate page in Qualtrics® that will not be linked to the data for the study. Each student can provide an email address that will be randomized to distribute an Amazon e-gift card to the student at the conclusion of each survey. The ARL will assist with the randomization of email addresses and distribute the e-gift card because the researcher is not aware of study participants. All study documents will be kept in a locked, secure cabinet for a period of three years in accordance with federal guidelines. All electronic data files will be stored in a password-protected file, and saved to a password-protected USB thumb drive for three years.

This USB thumb drive will be kept in a locked, secure cabinet when not in use. Data will be collected and aggregated by the ARL and will remove the email address and ten-digit phone number provided by the senior-level pre-licensure baccalaureate nursing students. The

*Define the level of privacy that will be afforded the research subjects (i.e., anonymity, confidentiality, or no expectation of privacy). Indicate how the level of privacy that is defined by the researcher is consistent with the study procedures and how their privacy will be protected within that framework. Federal regulations require researchers to maintain data and consent documents for three years. Please indicate you will do that and where the data will be stored.*

researcher will receive a Microsoft® Excel document that will contain no personally identifiable information of nursing students from the ARL. The participants will provide a ten-digit cell phone number and email address over the course of the study but will be de-identified and all participants will be provided with a new study ID number by the ARL. All study data will remain anonymous to the researcher and confidential to the ARL.

